2.2 Sample size calculations overview

Table 4 describes the minimum detectable effect size (MDES) estimates and sample sizes for the TISUK impact evaluation. The goal was to adopt conservative assumptions to allow for a well powered statistical analysis sufficient to detect an MDES below 0.20¹ and sub-population analysis.

Sample size estimations and assumptions

The goal is to calculate the required sample size for detecting a meaningful difference in the primary outcome measure of adolescent externalising behaviours. Key parameters involved in the calculation include the effect size, power, alpha level, and accounting for the clustered

¹ All YEF evaluations require a minimum detectable effect (MDES) below 0.20

design. Table 4 describes the sample size calculated using Stata 17© according to the following assumptions:

1. A pre-post zero correlation is assumed for externalising behaviours, as there are no reliable sources from which to base an estimate. Furthermore this represents the most conservative scenario for sample size estimation. Assuming a non-zero correlation would risk underestimating the required sample size if the assumed correlation is too high, we obtain a conservative sample size estimate for a covariance analysis by omitting this parameter and assuming a zero correlation. .
2. The SDQ (externalising scale) adolescent population mean is 6.0, and the assumed pooled Standard Deviation (SD) is 1.74², using the UK self-report population norms for 11-15 year olds³. Thus, to detect an effect size of 0.2 or greater, we need an SDQ externalising behaviours score difference of 6.0 (control) versus 5.66 (intervention). This difference requires 527 participants in each group, 1,054 for the whole sample.
3. Assuming 10% pupil-level attrition between baseline and follow-up requires a total sample size of 1,172.

Sample Size Calculation

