	70	0.1272	0.1284	0.1298	0.1317	0.1341
	60	0.1374	0.1385	0.1402	0.1422	0.1449

Rationale for Targeting 100 Schools

Targeting 100 schools and 16,000 students is justified by several considerations. First, a larger pool of schools increases the likelihood of recruiting a diverse population of school types (e.g., school-level of deprivation, FSM, different socioeconomic backgrounds) and student demographics, enabling robust subgroup analyses and generalizability of findings across various contexts. Second, a large overall sample size enhances statistical power to detect smaller but potentially meaningful intervention effects, minimising the risk of false negatives and providing reliable findings to inform future interventions. Third, the target sample size was selected to ensure sufficient power for the quasi-experimental design (QED) analysis focused on a targeted subgroup of students. Lastly, a larger sample size accommodates the cluster randomised trial design, accounting for potential clustering effects and maintaining adequate power for the primary analysis.

Table 4 displays the minimum detectable effect in the protocol according to the assumed parameters, target sample size, and the respective effect size after randomisation driven by the achieved number of responses on the primary outcome. Thus, while the MDES in the protocol is an estimation from the assumptions, the MDES estimated in the column 'Randomisation' corresponds to the actual achieved sample size at baseline in the primary outcome from the schools that were randomised. As we are adopting an intention-to-treat approach, the estimation includes responses from 4 schools that dropped out after randomisation.⁵ Those four schools that dropped out belong to the intervention group.

⁵ This means that now the number of schools in the trial are 74 with 4 dropping out from the intervention group after randomisation

Table 4 Sample size calculations and effects size

		Protocol	Randomisation
Minimum Detectable Effect Size (MDES)		0.1064	0.094
Pre-test/ post-test correlations	level 1 (participant)	n/a	n/a
	level 2 (cluster)	n/a	n/a
Intracluster correlations (ICCs)	level 1 (participant)	n/a	n/a
	level 2 (cluster)	0.03	0.015
Alpha		0.05	0.05
Power		0.8	0.8
One-sided or two-sided?		Two-sided	Two-sided
Average cluster size		160⁶	166⁷
Number of clusters	intervention	50	40
	control	50	38
	Total	100	78 ⁸

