⁶ Average school size in England is 986, average year size is 200 and accounting for a potential 20% not consenting, hence, cluster size 160.

⁷ This is the actual cluster average size

⁸ Although the initial plan was to allocate schools equally to the intervention and control groups at the randomisation stage, the achieved sample showed a slight difference due to attrition during the recruitment

		Protocol	Randomisation
Number of participants	intervention	8,000	6,391
	control	8,000	7,214
	Total	16,000	13,393 ⁹

The MDES calculations were performed using PowerUp! Tool, developed by Dong and Maynard (2013), which incorporates the formula below according to Bloom, Richburg-Hayes, and Black (2007), for the two-level cluster randomised controlled trials:

$$MDES = M_{n-k*-2} \sqrt{\left(\frac{\rho(1 - R_C^2)}{P(1 - P)J}\right) + \left(\frac{(1 - \rho)(1 - R_i^2)}{P(1 - P)Jm}\right)}$$

Employing this formula enables the inclusion of baseline covariates at the cluster (school) level, pupil level, or both. Our analysis strategy intends to use mean-centered baseline scores within the multilevel models at both the pupil and school levels. Incorporating a covariate at both levels - school and pupil - enhances the trial's precision, resulting in a reduced Minimum Detectable Effect Size (MDES) estimate compared to methodologies that employ only one covariate or none.

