2.3.8 Missing data

The proportion of missing data and patterns of missingness will be examined for the primary outcome only, externalising behaviour at six months post-randomisation. Levels of missing data will be reported along with any systematic occurrences of missing data observed in the dataset.

In trials, some participants are inevitably lost to follow-up. The sample size estimation assumed that 20%¹² of participants would not provide an evaluable 6-month follow-up assessment. We will explore the mechanism of missing data to establish whether the data can be considered missing completely at random or missing at random. For each arm, we will present baseline data for those who were followed up at 6 months and those who were lost to follow-up. A logistic regression analysis will be conducted to explore any systematic differences between the allocated groups. If the regression model does not identify any predictor variables, it suggests that the missing data can be considered missing at random.

To avoid loss of efficiency, missing outcome values will be imputed using multiple imputation if the proportion of missing data is greater than 5% and less than 40%. When less than 5% of data is missing, the proportion is considered negligible, and missing observations will be excluded. Multiple imputation methods may perform less well when a substantial amount of data is missing (e.g., more than 40% for the primary analysis). In such cases, the assumptions underlying the imputation become less plausible, and the interpretative limitations of the trial data will be discussed in the results section.

An initial variable reduction analysis will explore the relationship between all potentially prognostic baseline variables and whether a follow-up data point is missing. Only variables where there is an association (p-value > 0.10) will be included in the imputation model.

The number of imputations will be determined to ensure at least 96% statistical efficiency (RE), according to the formula below, where l is the fraction of missing values and M is the number of repetitions:

$$RE = \left(1 + \frac{\lambda}{M}\right)^{-1}$$

¹² This accounts for 10% attrition and 10% non-consent rate

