3.1 Design overview

A QED study, using a propensity score matching design, will be embedded within this trial to examine the targeted element of the intervention. In the intervention arm, some staff are given advanced training (Diploma level) to identify a more vulnerable CYP subgroup and provide extra targeted support. This individual intervention is estimated to be provided to about 75 CYP per school, 15 CYP per year group. In the main trial analysis, this group of CYP in Year 8 would become subsumed into the overall intervention group, with all baseline and follow-up data collected on outcomes included in the main trial. Staff who participate in the diploma training will already have identified most young people who would potentially benefit from more intensive support and, in the early stages of training, will be provided with tools to identify any additional young people. By the time of follow-up, at 15 months, this cohort of young people would have been identified and received at least nine months of intervention.

Assuming this group of vulnerable young people is about 15 per school, with a consent rate of 80%, the effective sample size will be 12 per school. Assuming our original aim of 100 schools in the trial, this gives 1,200 CYP across all schools, 600 in the treatment arm matched to 600 in the control arm.

The outcomes for this study will be the same individual pupil-level primary and secondary outcomes as for the main trial, for those that are provided with this individual or small group support in Year 8: the primary outcome is externalising behaviour at pupil level measured by the Strengths and Difficulties Questionnaires (SDQ) – Combined Conduct and Hyperactivity Scale. The secondary outcomes at pupil levels consist of internalising behaviour, prosocial behaviours, total difficulties, non-psychotic psychological distress, well-being, sense of connectedness, exclusions and suspensions, and school attendance.

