3.2 Sample size calculations

Sample size estimation and assumptions

The sample size calculation is designed to detect a difference of 0.2, YEF's expected maximum MDES value for efficacy evaluations. To detect this difference with 80% power, an alpha of 0.05 and a two-sided test, at least 527 CYP in each group are required, totalling 1,054 CYP.

For the PSM, the sample size estimations starts from the assumption of 15 CYP on average per school at baseline, assuming a follow-up rate of 80% to account for attrition and consent. The harmonic mean of CYP per year group receiving more intensive support is estimated to be 15. Using this and an ICC of 0.03, the estimated clustered design effect is 1.45. This inflates our required sample to 1,528. With 100 schools, 15 participants per class provide a sample of 1500. Incorporating the inverse propensity score weights will reduce the size of the overall sample by a conservative estimate of 30%, resulting in a required sample of 1,070.

Table 7 indicates the impact of different group sizes (pupils per cluster) on the number of schools needed in the intervention arm of the PSM analysis. The table shows that with 15 pupils per cluster, data from at least 36 intervention schools are required. At the lower end, with 10 pupils per cluster, data from 48 schools would be required. If the follow-up rate is 80% as anticipated, 12 pupils per school will be available, requiring circa 42 schools in each arm of the study. While the target is to maintain 50 schools in each arm, these conservative estimates should be considered.

At the point where the PSM is conducted, the pre- and post-test correlation for the primary outcome can be estimated and incorporated into the sample size calculation, potentially adjusting the required sample size.

Table 7 Impact of differential cluster size on the proportion of schools retained for the intervention group

Pupils	15	14	13	12	11	10
Base sample	527	527	527	527	527	527
Design effect (DE)	1.45	1.42	1.39	1.36	1.33	1.30
Adjusted sample	764	748	733	717	701	685
Sample adjusted for IPW	535	524	513	502	491	480
Number of intervention schools	36	37	39	42	45	48

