Table 8 displays the effect size based on the assumption of 12 CYP per cluster at follow-up, assuming 15 at baseline, accounting for attrition and consent. This is a conservative estimate. The second column "Randomisation" displays the effect size assuming 12 CYP per cluster given the number of schools achieved and the observed ICC at baseline. Thus, the total number of participants is an estimation.

Table 8 Sample size calculations - QED

		Protocol	Randomisation
Minimum Detectable Effect Size (MDES)		0.17	0.20
Pre-test/ post-test correlations	level 1 (participant)	n/a	n/a
	level 2 (cluster)	n/a	n/a
	level 1 (participant)	n/a	n/a

		Protocol	Randomisation
Intracluster correlations (ICCs)	level 2 (cluster)	0.03	0.015
Alpha		0.05	0.05
Power		0.8	0.80
One-sided or two-sided?		Two	Two
Average cluster size (if clustered)		12	12
Number of clusters (schools)	Intervention	50	40
	Control	50	38
	Total	100	78
Number of participants	Intervention	600	456
	Control	600	480
	Total	1,200 (without weighting)	936

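### The 80% that takes 15 targeted pupils to 12 is defined in two ways, and on the 74 schools still in the trial the QED's achieved MDES slightly exceeds 0.20 under either definition

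*SAP*

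**What the plan says.** **QED overview (SAP 3.1).** The section starts from 15 pupils: "Assuming this group of vulnerable young people is about 15 per school". It then applies one loss: "with a consent rate of 80%, the effective sample size will be 12 per school". Attrition is not mentioned in this step.

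**QED sample size (SAP 3.2).** The same 15 is reduced by the same 80%, now described as "assuming a follow-up rate of 80% to account for attrition and consent". The text introducing Table 8 repeats this: "12 CYP per cluster at follow-up, assuming 15 at baseline, accounting for attrition and consent". Protocol Appendix 2 also uses the combined description.

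**Main trial.** The footnote to SAP Table 4 spends the full 20% on consent: "accounting for a potential 20% not consenting, hence, cluster size 160". Assumption 3 of SAP 2.2 takes attrition separately: "Assuming 10% pupil-level attrition between baseline and follow-up requires a total sample size of 1,172". A footnote in SAP 2.3.8 instead splits one 20% loss into two parts: "This accounts for 10% attrition and 10% non-consent rate".

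**Schools.** The Randomisation column of Table 8 uses 78 schools (40 intervention, 38 control), an observed ICC of 0.015 and 12 pupils per school, and reports an MDES of 0.20. SAP 2.2 says of the main-trial figure that "the estimation includes responses from 4 schools that dropped out after randomisation", all four from the intervention arm, leaving 74. It justifies this by intention to treat. SAP 3.3 identifies the QED's treated pupils by asking for details of those receiving support every six months. SAP 3.4.8 bases the QED groups on complete data.

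**The concern.** The cluster size of 12 carries the whole QED calculation, and its meaning changes between adjacent sections. If 12 is what remains after consent only, attrition still has to come off and the analysed number is lower. If 12 already includes attrition, the figure is consistent but the overview is misworded.

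The count of schools is a second weakness in the same table column. Keeping departed schools in the count may be defensible for an intention-to-treat analysis of pupils surveyed at baseline. It is harder to defend for a treated group that exists only if the school reports it and the pupils have follow-up data.

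SAP 3.2 describes 0.2 as the funder's maximum MDES for efficacy evaluations, and Table 8 lands exactly on it. With no slack, either issue takes the figure past the limit, and a null QED result would be read as a little better powered than it is.

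**Working it through.** **Formula.** This is the SAP 2.2 formula with no covariate R-squared, because Table 8 enters no pre-post correlation:

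MDES = M × sqrt( ρ/[P(1−P)J] + (1−ρ)/[P(1−P)J·m] )

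Here J is the number of schools, P the intervention share, m the pupils per school, ρ the ICC, and M = t(0.975, J−2) + t(0.80, J−2). SAP 2.2 gives the formula for the main trial. Its use for the QED is inferred, and supported by the fact that it reproduces Table 8's achieved figure.

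**Inputs.** ρ = 0.015, two-sided alpha 0.05 and power 0.80 (Table 8). Schools are 40 + 38 = 78 as randomised, or 36 + 38 = 74 remaining (SAP 2.2).

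**Pupils per school under each definition of the 80%.**
- Consent and attrition combined: 15 × 0.80 = 12. The 10% + 10% footnote agrees: 15 × (1 − 0.20) = 12, or 15 × 0.9 × 0.9 = 12.15 if compounded.
- Consent only, followed by the main trial's 10% attrition: 15 × 0.80 × 0.90 = 10.8.

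**Reproducing the plan's figure.** 78 × 12 = 936 matches the participant total in Table 8.
- P(1−P)J = (40 × 38)/78 = 19.487, and M = 1.992 + 0.846 = 2.838.
- School term: 0.015/19.487 = 0.000770.
- Pupil term: 0.985/(19.487 × 12) = 0.004212.
- MDES = 2.838 × sqrt(0.004982) = 2.838 × 0.07058 = 0.2003.

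This agrees with the stated 0.20. Normal quantiles give 0.198.

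**74 schools, m = 12.**
- P(1−P)J = (36 × 38)/74 = 18.486, and M = 2.840.
- MDES = 2.840 × sqrt(0.000811 + 0.004440) = 2.840 × 0.07247 = 0.206. Normal quantiles give 0.203.

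**74 schools, m = 10.8.**
- MDES = 2.840 × sqrt(0.000811 + 0.004934) = 2.840 × 0.07580 = 0.215.

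**Summary** (power at an effect of 0.20, noncentral t with J−2 degrees of freedom):

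| Schools | Pupils per school | MDES | Power for 0.20 |
|---|---|---|---|
| 78 | 12 | 0.2003 | 79.9% |
| 78 | 10.8 | 0.2095 | 76.3% |
| 74 | 12 | 0.206 | 77.7% |
| 74 | 10.8 | 0.215 | 74.0% |

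**The case against.** The strongest reply is that the text producing the MDES does include attrition. SAP 3.2, the introduction to Table 8 and Protocol Appendix 2 all treat 12 as the number at follow-up. Only one overview sentence calls the 80% a consent rate, and the 10% + 10% footnote supports the combined reading. This stands. A reader might infer from SAP 3.1 that attrition is never removed in the QED, but the calculation sections say otherwise. The consent-only result is therefore conditional. A reader might also apply two separate 80% rates, one for consent and one for follow-up. No section states both, and the follow-up rate in SAP 3.2 already includes consent.

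A second reply is that Table 8 is conservative because it assumes zero pre-post correlation while the model adjusts for the baseline outcome. That is a fair point about the likely precision of the analysis. At 74 × 12, an R-squared of 1 − (0.20/0.2058)² ≈ 0.056 at both levels (a correlation of about 0.24) would restore 0.20. At 74 × 10.8 about 0.14 (a correlation of about 0.37) would be needed. These are assumed values; the plan gives no such correlation. They do not correct a table built on zero.

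Third, comparison pupils are selected after follow-up and weighted, so 10% attrition need not apply equally to both arms. Applying it to the intervention arm only (36 schools × 10.8, 38 × 12) gives 0.211, still above 0.20. If weighting left an effective 24 controls per school, which is purely an assumption, the figure would be 0.189. Variable weights could equally lose precision, as SAP 3.3 acknowledges.

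Finally, the loss of four schools is disclosed, the column is headed as the position at randomisation, and its participant total is labelled an estimate. The disclosure is in the main-trial section, and its intention-to-treat rationale does not carry over to a complete-data comparison of reported recipients.

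**Conclusion.** The inconsistency is real: one 20% loss is described as consent only in SAP 3.1 and as consent plus attrition in SAP 3.2, and the main-trial text supports each reading in a different place. Taken alone, the wording conflict does not show Table 8 to be wrong, since 0.20 reproduces at 78 schools of 12.

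On the 74 remaining schools the MDES is about 0.206 under the combined definition and about 0.215 under the consent-only definition with 10% attrition. It therefore exceeds 0.20 either way, by about 0.006 to 0.015, and power for 0.20 is about 78% or 74% rather than 80%. These figures rest on ICC 0.015, equal numbers per school in both arms, zero pre-post correlation and no contribution from the four departed schools. They come before any gain from baseline adjustment or any loss from weighting.

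The shortfall is small. It does not show that the analysis as run will miss 0.20, nor that the QED is badly underpowered. It shows that the tabulated figure should be restated.

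**What to change.** 1. Define the 80% once and use that definition in SAP 3.1, SAP 3.2, the Table 8 text and Protocol Appendix 2. State the assumed consent rate and attrition rate separately. The authors should say which reading they intended.
2. Align the main-trial wording in the same edit: the Table 4 footnote and assumption 3 in SAP 2.2 against the footnote in SAP 2.3.8.
3. Recompute the achieved QED column of Table 8 on 36 intervention and 38 control schools. Report about 0.206 if 12 includes attrition, or about 0.215 if 12 is after consent only and 10% attrition follows.
4. Add a sentence that the 0.20 maximum is slightly exceeded under the tabulated assumptions, before baseline adjustment and weighting. SAP 3.2 already plans to estimate the pre-post correlation when the matching is done, and the MDES can be updated then.

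The cost is a few lines of wording and one table column. Design, data collection and analysis model do not change, and the published figure becomes slightly less favourable.

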3.2 Sample size calculations

Sample size estimation and assumptions

The sample size calculation is designed to detect a difference of 0.2, YEF's expected maximum MDES value for efficacy evaluations. To detect this difference with 80% power, an alpha of 0.05 and a two-sided test, at least 527 CYP in each group are required, totalling 1,054 CYP.

For the PSM, the sample size estimations starts from the assumption of 15 CYP on average per school at baseline, assuming a follow-up rate of 80% to account for attrition and consent. The harmonic mean of CYP per year group receiving more intensive support is estimated to be 15. Using this and an ICC of 0.03, the estimated clustered design effect is 1.45. This inflates our required sample to 1,528. With 100 schools, 15 participants per class provide a sample of 1500. Incorporating the inverse propensity score weights will reduce the size of the overall sample by a conservative estimate of 30%, resulting in a required sample of 1,070.

Table 7 indicates the impact of different group sizes (pupils per cluster) on the number of schools needed in the intervention arm of the PSM analysis. The table shows that with 15 pupils per cluster, data from at least 36 intervention schools are required. At the lower end, with 10 pupils per cluster, data from 48 schools would be required. If the follow-up rate is 80% as anticipated, 12 pupils per school will be available, requiring circa 42 schools in each arm of the study. While the target is to maintain 50 schools in each arm, these conservative estimates should be considered.

At the point where the PSM is conducted, the pre- and post-test correlation for the primary outcome can be estimated and incorporated into the sample size calculation, potentially adjusting the required sample size.

Table 7 Impact of differential cluster size on the proportion of schools retained for the intervention group

Pupils	15	14	13	12	11	10
Base sample	527	527	527	527	527	527
Design effect (DE)	1.45	1.42	1.39	1.36	1.33	1.30
Adjusted sample	764	748	733	717	701	685
Sample adjusted for IPW	535	524	513	502	491	480
Number of intervention schools	36	37	39	42	45	48

Table 8 displays the effect size based on the assumption of 12 CYP per cluster at follow-up, assuming 15 at baseline, accounting for attrition and consent. This is a conservative estimate. The second column "Randomisation" displays the effect size assuming 12 CYP per cluster given the number of schools achieved and the observed ICC at baseline. Thus, the total number of participants is an estimation.

Table 8 Sample size calculations - QED

		Protocol	Randomisation
Minimum Detectable Effect Size (MDES)		0.17	0.20
Pre-test/ post-test correlations	level 1 (participant)	n/a	n/a
	level 2 (cluster)	n/a	n/a
	level 1 (participant)	n/a	n/a

		Protocol	Randomisation
Intracluster correlations (ICCs)	level 2 (cluster)	0.03	0.015
Alpha		0.05	0.05
Power		0.8	0.80
One-sided or two-sided?		Two	Two
Average cluster size (if clustered)		12	12
Number of clusters (schools)	Intervention	50	40
	Control	50	38
	Total	100	78
Number of participants	Intervention	600	456
	Control	600	480
	Total	1,200 (without weighting)	936

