The propensity score is the probability of receiving the intervention conditional on measured participant covariates. It is, in essence, a balancing score. If we have two populations, the intervention and control populations, both of which have a similar propensity score, the distribution of baseline covariates will be the same in the intervention and control groups. Hence, we can remove the effects of confounding by comparing participants who share a propensity score, this is analogous to that induced by randomisation in RCT's.

A counterfactual control group will be derived using PSM to draw causal inferences of the relative effect of the intervention. A probit regression model will be employed, blind to group source. Callipers of width 0.2 of the standard deviation of the width of the logit propensity score will be employed to maximise matching. Once the propensity scores have been generated, they will be incorporated into the primary and secondary analysis using inverse propensity score weights (IPSW) because this will reduce the sample size required for the control group.

Sample size estimation and assumptions

The sample size calculation is designed to detect a difference of 0.2²⁰. To detect this difference with 80% power, an alpha of 0.05 and a two-sided test require 527 in each group, a total of 1,054.

For the PSM, the sample size estimations starts from the assumption of 15 CYP on average per school at baseline, assuming a follow-up rate of 80% to account for attrition and consent. The harmonic mean of CYP per year in a group receiving more intensive support is estimated to be 15. We can use this and our ICC of 0.03 to estimate the clustered design effect as 1.45. This inflates our required sample to 1,528. With 100 schools, 15 participants per class provide a sample of 1,500. Incorporation of the inverse propensity score weights will reduce the size of the control group by a conservative estimate of 30%. Therefore, an overall sample of 1,070 would be required.

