The propensity score is the probability of receiving the intervention conditional on measured participant covariates. It is, in essence, a balancing score. If we have two populations, the intervention and control populations, both of which have a similar propensity score, the distribution of baseline covariates will be the same in the intervention and control groups. Hence, we can remove confounding effects by comparing participants who share a propensity score. This is analogous to that induced by randomisation in RCTs.

For the propensity score, the covariates for the matching will be socio-demographic variables such as sex, age, ethnicity, FSM, attendance, exclusions, suspensions and pre-test outcomes for the primary and secondary outcomes. As is often the case in PSM, the selection of the variables will depend on which model delivers the best balance in the matched sample.

A counterfactual control group will be derived using PSM to draw causal inferences of the relative effect of the intervention. A probit regression model will be employed. Callipers of width 0.2 of the standard deviation of the width of the logit propensity score will be employed to maximise matching. Once the propensity scores have been generated, they will be incorporated into the primary and secondary analysis using inverse propensity score weights (IPSW), because this will reduce the sample size required for the control group. One potential limitation of weighting approaches, akin to Horvitz-Thompson's estimation, is the potential for a substantial increase in variance when dealing with extreme weights (i.e. when estimated propensity scores approach 0 or 1). This increased variance is justified if the model is

appropriately specified and the weights are accurate. However, a concern arises when some extreme weights are more closely linked to the estimation process rather than the true underlying probabilities. To mitigate the impact of extreme weights, we would consider weight trimming as a solution, whereby weights exceeding a certain maximum value are capped at that maximum (Stuart, 2010). Robustness check through other matching techniques will allow us to test the sensitivity of this approach to increase in variance. Other matching approaches will include exact matching, Nearest-Neighbour matching, Mahalanobis distance, PSM with different calliper widths, and CEM, as discussed further in section 3.4.3 below.

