3.4.5 Subgroup analyses

Sub-group analysis will be conducted to estimate how the treatment effects vary within groups. This means estimating heterogeneous effects, namely, conditional average treatment effects (CATE). The groups consist of sex, ethnicity and FSM. We will aim to minimise the number of strata within each category whenever applicable and necessary. For example, ethnicity will be divided into minority and non-minority to maximise statistical power.

After passing the balancing test and robustness checks, the approach will first achieve a matched sample, thus obtaining the average treatment effect on the treated (ATET). Then, we will condition the ATET on the respective group variables to obtain treatment effect by stratum, namely the CATE.

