3.4.8 Missing data

As the generation of intervention and comparison groups are based on complete data, we do not account for missing data.

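### QED study: the stated power figures contain errors, the 30% weighting discount is underived and inconsistently applied, and the weights conflict with the named estimand

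*SAP*

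**What the plan says.** SAP 3.2 starts from 527 pupils per group for an effect of 0.2 at 80% power, two-sided 5%. It multiplies the total by a design effect of 1.45 (15 pupils, ICC 0.03) to reach 1,528, and then takes off 30% to reach 1,070: "Incorporating the inverse propensity score weights will reduce the size of the overall sample by a conservative estimate of 30" per cent. Protocol Appendix 2 makes the same cut but describes it differently: "Incorporation of the inverse propensity score weights will reduce the size of the control group by a conservative estimate of 30" per cent. SAP Table 7 (Protocol Appendix Table 3) takes the 30% off the per-arm sample used to count intervention schools. At the anticipated follow-up, "12 pupils per school will be available, requiring circa 42 schools in each arm of the study".

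SAP Table 8 gives a Protocol MDES of 0.17 (50 + 50 schools, 12 pupils, ICC 0.03), as does Protocol Appendix Table 2. Its second column "displays the effect size assuming 12 CYP per cluster given the number of schools achieved", namely 40 + 38 schools at ICC 0.015, with MDES 0.20. SAP 2.2, footnote 5, records later losses: "This means that now the number of schools in the trial are 74 with 4 dropping out from the intervention group after randomisation".

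On the analysis, SAP 3.3 brings the propensity scores in "using inverse propensity score weights (IPSW), because this will reduce the sample size required for the control group", and SAP 3.4.1 weights every participant in the primary model. SAP 3.4.5 describes forming a matched sample, "thus obtaining the average treatment effect on the treated (ATET"). SAP 3.4.8 says the two groups "are based on complete data, we do not account for missing data".

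**The concern.** Two matters are at stake. The first is whether the QED has the precision claimed for it against the funder's 0.20 ceiling. The MDES cell, the base sample and the discount all feed that claim, and intervention schools have since been lost.

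The second is what the QED would estimate. Inverse propensity weights on both groups target the effect of support averaged over all pupils (ATE). The QED asks about the vulnerable pupils who are selected for support (ATET). At about 12 supported pupils in a year group of about 166 (7%), these are different questions, and the ATE version leans on the few supported pupils who resemble the average pupil.

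**Working it through.** **Method check.** The formula in SAP 2.2, without covariates, is MDES = M × √[ρ/(P(1−P)J) + (1−ρ)/(P(1−P)Jm)]. M = 1.960 + 0.842 = 2.802 (z), or the t version with J − 2 degrees of freedom. For the main trial (J = 100, m = 160, ρ = 0.03), 2.802 × 0.03798 = 0.1064, exactly the stated figure.

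**Table 8, Protocol column** (J = 100, P = 0.5, ρ = 0.03):
- m = 12: 2.802 × 0.06658 = 0.187 (z); 0.188 (t)
- m = 15: 2.802 × 0.06154 = 0.172 (z); 0.174 (t)

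The stated 0.17 therefore matches 15 pupils, not 12. ICC 0.015 with 12 pupils would give 0.175 (z), but the column states 0.03.

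**Table 8, Randomisation column** (40 + 38, m = 12, ρ = 0.015): 0.198 (z), 0.200 (t). The stated 0.20 reproduces. The participant counts are reversed: 40 × 12 = 480 is the intervention arm and 38 × 12 = 456 the control arm, but the table lists 456 and 480.

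**Schools remaining** (36 + 38, m = 12):

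| ICC | z | t | Power at 0.20 (t) |
|---|---|---|---|
| 0.015 | 0.203 | 0.206 | 77.7% |
| 0.03 | 0.217 | 0.220 | 72.2% |

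For 40 + 38 at ICC 0.015 the power is 79.9%.

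**Base sample.** n per group = 2(1.960 + z)²/0.2². At 80% power this is 392.4, so about 394 with a small-sample allowance. At 90% it is 525.4. The 527 is thus about the 90% figure; its power at 0.2 is 90.1%.

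**The 30% discount.** 1,528 × 0.7 = 1,070 cuts both groups. A control-only cut, as the Protocol words it, would give 764 + 0.7 × 764 = 1,299. Table 7 cuts the intervention arm (764 to 535).

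**Table 7 at 12 pupils.**
- As stated: 527 × 1.36 × 0.7 / 12 = 41.8, shown as 42. It reproduces.
- Base 394, no discount, 1:1, design effect 1 + 0.03 × 11 = 1.33: 394 × 1.33 / 12 = 43.7, so 44.
- The same at the observed ICC 0.015, design effect 1.165: 394 × 1.165 / 12 = 38.3, so 38 to 39.

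The errors nearly cancel because 527 × 0.7 = 369 lies close to 394. All of these counts exceed 36.

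**Estimand and weights, side by side.**
- SAP 3.3: weights likened to Horvitz-Thompson estimation, with trouble at scores near 0 or 1. This describes ATE weights. Trimming is allowed.
- SAP 3.4.1: inverse propensity weighting of all participants in the primary model.
- SAP 3.4.3: one-to-one matching as the main technique, inverse weighting among the robustness checks, and a reference to the ATE.
- SAP 3.4.5: ATET. The parallel text in Protocol Appendix 2 has the ATE.

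No weight formula is written anywhere.

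**MDES for ATET weighting.** With all control-school pupils weighted and control effective size E, MDES = M × √[ρ/36 + (1−ρ)/(36 × 12) + ρ/38 + (1−ρ)/E]. E is not in the documents; assume 2,000 to 4,000. At ρ = 0.015 the MDES is 0.162 to 0.168 (z) or 0.164 to 0.170 (t). At ρ = 0.03 it is 0.180 to 0.185 (z) or 0.182 to 0.187 (t).

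**The case against.** Several points on the other side stand.

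A reader might infer that weighting controls can never reduce the supported sample needed. That is false. With k effective controls per supported pupil, the supported sample needed is n(1 + 1/k)/2, and k = 2.5 gives a factor of 0.70 before clustering. A cut of this size is possible when the whole control pool is used. What fails is the documentation: there is no derivation, there are three different targets, and Table 8 is a 1:1 calculation of 600 against 600.

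A reader might also infer that the QED clearly misses the funder's limit. At ICC 0.015 the excess is only 0.003 to 0.006. It assumes no covariate gain, although the model adjusts for baseline and SAP 3.2 expects to bring in the pre-post correlation later. An assumed R² of 0.10 at both levels gives 0.195; 0.25 gives 0.178. Nor does the corrected Protocol MDES of 0.19 breach 0.20.

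Dropping the discount alone would suggest 60 schools (527 × 1.36 / 12 = 59.7), but that keeps the 90%-power base and overstates the need.

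Finally, 40 is the right count for a column headed Randomisation, and that total is described as an estimate. The documents do not firmly prescribe ATE weights either: they also describe calliper matching, one-to-one pairs and trimming. The supportable charge is contradiction.

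**Conclusion.** The point holds as a set of correctable errors plus an unresolved estimand. The Protocol MDES is 0.19, not 0.17. The 527 is about a 90%-power base labelled 80%. The 30% is unsupported and inconsistently applied, and Table 8's arm counts are reversed. The Randomisation MDES of 0.20 and Table 7's arithmetic, given its inputs, do reproduce.

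At 12 pupils per school, 1:1, the 36 intervention schools left fall short of the 42 stated, of 44 corrected at ICC 0.03, and of 38 to 39 at ICC 0.015. The resulting MDES of 0.203 to 0.206 is marginal. It rests on zero covariate gain and on supported pupils in the four departed schools being unavailable. The second assumption is reasonable because schools must report who received support every six months (SAP 3.3).

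The estimand conflict matters more for interpretation. If ATE weights were used, the result would not answer the question about the vulnerable group. The documents do not allow the size of that difference to be calculated. Should-fix, for an embedded secondary study.

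**What to change.** 1. Restate the Protocol MDES as 0.19 in SAP Table 8 and Protocol Appendix Table 2.
2. Replace 527 by 394 as the 80%-power base, remove the 30% discount, and recompute Table 7 and Protocol Appendix Table 3.
3. In Table 8, correct the reversed counts and add a 36 + 38 school column (MDES 0.20 to 0.21 at ICC 0.015, labelled as 1:1).
4. Name the ATET as the single QED estimand and write out its weights: 1 for supported pupils and p/(1−p) for control-school pupils, where p is the propensity score. Align SAP 3.3, 3.4.1, 3.4.3 and 3.4.5 and Protocol Appendix 2.
5. Report the MDES for that analysis as the operative figure instead of the 1:1 value. It is about 0.16 to 0.17 at ICC 0.015, or 0.18 to 0.19 at 0.03, if the control effective size is 2,000 to 4,000. State that size as an assumption.
6. Secondary: estimate the propensity score on all pupils with baseline data, and extend the main trial's multiple imputation to missing QED follow-up, so that group membership does not depend on complete data.

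The cost is revised wording, recalculated tables and a slightly less favourable stated 1:1 MDES. No new data are needed. The estimand should be settled before follow-up outcomes are analysed.
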